7.4. Blinding

This will be a double blind (sponsor unblind) study and the following will apply.

- The investigator or treating physician may unblind a participant's treatment assignment **only in the case of an emergency** OR in the event of a serious medical condition when knowledge of the study treatment is essential for the appropriate clinical management or welfare of the participant as judged by the investigator.
- It is preferred (but not required) that the investigator first contacts the Medical Monitor or appropriate GSK study personnel to discuss options **before** unblinding the participant's treatment assignment.
- If GSK personnel are not contacted before the unblinding, the investigator must notify GSK as soon as possible after unblinding, but without revealing the treatment assignment of the unblinded participant, unless that information is important for the safety of participants currently in the study.
- The date and reason for the unblinding must be fully documented in the CRF

A participant will be withdrawn if the participant's treatment code is unblinded by the investigator or treating physician. The primary reason for discontinuation (the event or condition which led to the unblinding) will be recorded in the CRF.

- GSK's Global Clinical Safety and Pharmacovigilance (GCSP) staff may unblind the treatment assignment for any participant with an SAE. If the SAE requires that an expedited regulatory report be sent to one or more regulatory agencies, a copy of the report, identifying the participant's treatment assignment, may be sent to investigators in accordance with local regulations and/or GSK policy.
- Members of the GSK study team will be unblinded for in-stream data reviews and the interim analyses as appropriate. This may include the study statistician, programmers, physician project leader, Muscle Metabolism Discovery Performance Unit leader, safety review team and other decision makers. At the time of interim analysis, access to the randomization will be restricted to randomization numbers that have been assigned at the time of data cut-off.

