10. STATISTICAL CONSIDERATIONS

Unblinded data will be reviewed in-stream by the study team. A Bayesian predictive approach using a non-informative prior will be used for the assessment of futility of the strength endpoint at an interim analysis. Although strength is the primary endpoint for the assessment of futility, the decision to continue or stop recruitment will be based on the totality of the data including strength, lean mass, functional endpoints, safety and tolerability.

After study completion, a Bayesian analysis using non-informative priors will be used to estimate posterior and posterior predictive distributions, as appropriate, for strength, lean mass and the functional endpoints to inform decision making. A multivariate Bayesian approach will be employed, data permitting

In addition, the effects of GSK2881078 relative to placebo on strength, lean mass and functional endpoints (i.e., incremental and endurance shuttle walk tests, and SPPB) will be evaluated using an estimation approach where point estimates and associated 90% confidence intervals (CI) will be constructed.

Descriptive statistics will be used to address safety, tolerability, PRO and PK objectives.

Data for male and female subjects will be analyzed separately. Depending on recruitment rates, analysis and reporting may be completed at different times for males and females.

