10.3.4. Interim Analyses

The Reporting and Analysis Plan will describe the planned interim analyses in greater detail.

In-Stream Review

Safety, tolerability, strength, lean mass, and functional endpoint data will be reviewed by the GSK study team on an ongoing basis throughout the study for the purpose of internal decision making. These reviews can include individual participant data, summaries by treatment group and graphical displays. GSK staff will be unblinded (See Section 7.3). Participants and all site personnel will be blinded to participant randomization.

Preliminary safety, strength, lean mass, functional endpoint and PK results may be reported prior to database freeze for the purposes of safety review by GSK and where required by regulatory bodies.

Interim Analysis

An interim analysis for the assessment of futility is planned. It is anticipated that a formal declaration of futility would not be made before at least 10 participants per group have completed dosing and all key study assessments. However, if at any time it is determined

that the probability of a successful outcome is sufficiently low, recruitment could be stopped. The primary endpoint for assessment of futility is strength. However, the decision to continue or stop recruitment will be made by the unblinded GSK clinical study team and SRT based on the evaluation of all available safety, efficacy, and tolerability data. Such decisions will be based on the totality of the data (including strength, lean mass, function, safety, and tolerability). The feasibility of making a decision to stop recruitment based on a futility analysis will be dependent on the recruitment rate. Whether recruitment is suspended for the interim analysis will be dependent on the recruitment rate. Assessment of futility will be done separately for female and male participants. A Bayesian predictive approach using a non-informative prior will be used to assess the futility of % change from baseline strength at 13 weeks.

The futility criteria for strength will be based on the posterior predictive probability at the interim that the end of study difference in % change from baseline strength between GSK2881078 and placebo will achieve a positive outcome ($\geq 9\%$). If the predicted probability of achieving this positive outcome is too low in the context of all available data, then enrolment into the treatment arm(s) or cohort may be stopped.

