### 3. PLANNED ANALYSES

#### 3.1. Final Analyses

The final planned primary analyses will be performed after the completion of the following sequential steps:

1. All participants have completed the study as defined in the protocol
2. All required database cleaning activities have been completed and final database release (DBR) and database freeze (DBF) has been declared by Data Management.
3. All criteria for unblinding the randomization codes have been met.
4. Randomization codes have been distributed according to RandAll NG procedures.

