#### 4.1. Protocol Deviations

Important protocol deviations (including deviations related to study inclusion/exclusion criteria, conduct of the trial, patient management or patient assessment) will be summarised and listed.

Important deviations which result in exclusion from the analysis population will also be summarised and listed. (Please refer to [Appendix 1](#): Protocol Deviation Management and Definitions for Per Protocol Population).

Protocol deviations will be tracked by the study team throughout the conduct of the study in accordance with the 'Protocol Deviation Specification-version 6.0 dated 28 Nov 2019

- Data will be reviewed prior to unblinding and freezing the database to ensure all important deviations and deviations which may lead to exclusion from the analysis are captured and categorised on the protocol deviations dataset. It will not be possible to identify whether subjects received a different treatment to the one they were randomised to until post unblinding, hence this protocol deviation will be identified after unblinding the database.
- A blinded data review meetings (BDRM) will be handled before the final database release (DBR)
- This dataset will be the basis for the summaries and listings of protocol deviations.

A listing of all inclusion/exclusion criteria deviations will also be provided. This listing will be based on data as recorded on the inclusion/exclusion page of the eCRF.

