### 8.2. Adverse Events of Special Interest Analyses

The table in [Section 12.6.3](#) (“Safety”) presents the Adverse Events of Special Interest (AESI) and the groups of terms that they comprise. AESI which are not standardized MedDRA queries (SMQs) comprise a selection of PTs defined by GSK. The final list of AESIs, and the PTs that contribute to each of the AESIs, will be provided by Safety and Medical Governance (SMG), using the MedDRA version current at the time of reporting. This list will be finalized prior to unblinding the database.

Changes to the MedDRA dictionary may occur between the start of the study and the time of reporting. Furthermore, emerging data from on-going studies may highlight additional AESI. Therefore, the list of AESI, and the terms included for each AESI, will be based on the safety review team (SRT) agreements in place at the time of reporting. The details of the planned displays are provided in [Appendix 11](#): List of Data Displays.

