## 12. APPENDICES

### 12.1. Appendix 1: Protocol Deviation Management and Definitions for Per Protocol Population

#### 12.1.1. Exclusions from Per Protocol Population

The criteria for subject exclusion from the Per Protocol population are based on 'the Protocol Deviation Specification-version 2.0-31August 2018'. Refer to the latest version of the rules document prior to finalisation of the per protocol population.

The following criteria define the protocol deviations Potential protocol deviations leading to exclusion from PP population will be reviewed by the study team to confirm that they meet these criteria. This review will occur before the clinical database has been frozen for analysis. Note: None of the protocol deviations need the data unblinding to take the decision whether the subject data to be excluded from analysis or not. So, the protocol deviation meeting post unblinding won't be conducted.

A subject meeting any of the following criteria will be excluded from the Per Protocol population:

Number	Exclusion Description
01	Inclusion #1 – Subject not 50-75 years of age inclusive
02	Inclusion #3 – Did not have Confirmed Diagnosis of COPD
03	Inclusion #4 – SPPB: Score of "0" on any component of the SPPB or Timed Chair Stand Score is < 1 and > 3
04	Inclusion #5 – BMI not within 18-32 kg/m  (inclusive)
05	Inclusion #6 – not current smokers or former smokers with a cigarette smoking history of <10 pack years
06	Exclusion #1-7 – Prohibited Medical Conditions
07	Exclusion #8-10 – Prohibited Treatments
08	Exclusion #11 – Prohibited Prior/Current Clinical Study Experience
09	Exclusion #12-13 – Key laboratory tests out of range
10	Exclusion #14 – ECG values above ranges (QTc > 480, QTcB/F > 450)
11	Exclusion #15 – Positive HIV antibody test
12	Any other deviations from inclusion/exclusion criteria which could impact the efficacy assessment.
13	Experience an exacerbation, which needed treatment with steroids during the treatment phase of the study
14	Not completing the Day 80 PROactive endpoint, Week 13 (Day 90) lean mass and all of the functional assessments (leg press strength, peak performance from Incremental shuttle walking test, Constant Work Rate (CWR) duration from endurance shuttle walking test, total SPPB score and handgrip strength).
15	Permanent discontinuation of the treatment during the study treatment period (This check must will be performed by Statistics and Programming).

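### The SAP calls the deviation review blinded and has the study team confirm per-protocol exclusions, but the protocol allows that team by-arm data throughout and no firewall is described

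*SAP*

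**What the plan says.** The SAP reads as if the sponsor were blind until the final analysis.

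- Section 4.1 (Protocol Deviations): "Data will be reviewed prior to unblinding and freezing the database to ensure all important deviations" are captured, and "A blinded data review meetings (BDRM) will be handled before the final database release (DBR"). It adds that a participant who received the wrong treatment cannot be recognised until after unblinding.
- Section 12.1.1 (per-protocol exclusions): "Potential protocol deviations leading to exclusion from PP population will be reviewed by the study team". This happens before the freeze, against 15 listed rules, with no meeting after unblinding.
- Section 3.1 (Final Analyses): codes are distributed only after database freeze and once "All criteria for unblinding the randomization codes have been met".
- Section 8.2 (adverse events of special interest, AESI): Safety and Medical Governance supplies the terms, resting on Safety Review Team (SRT) agreements. "This list will be finalized prior to unblinding the database".

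The protocol describes something different.

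- Section 10: "Unblinded data will be reviewed in-stream by the study team".
- Section 10.3.4: strength, lean mass, function and safety are reviewed on a continuing basis. "These reviews can include individual participant data, summaries by treatment group and graphical displays". The section says sponsor staff will be unblinded, while participants and site personnel stay blinded.
- Section 7.4: "Members of the GSK study team will be unblinded for in-stream data reviews and the interim analyses as appropriate". The statistician, programmers and SRT are named as possible members of that group.
- Section 5.1: both the clinical study team and the SRT are named as in-stream reviewers of unblinded data.

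**The concern.** The per-protocol analysis is useful as a supportive check only if membership is settled without regard to treatment arm and response. The SAP asserts this by calling the review blinded, yet it gives the confirming step to a body that the protocol allows to see both. If the study report repeats the SAP's wording, it will describe a safeguard that the documents do not establish. The same question arises, more weakly, for the AESI groupings, because the SRT is also an in-stream reviewer.

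**Working it through.** **1. Who decides, and what may they see?**

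| Decision | Deciding body in the SAP | SAP timing | Access under the protocol |
|---|---|---|---|
| Deviation review | Meeting called blinded; attendees not stated (4.1) | Before unblinding | Not stated for this meeting |
| Per-protocol exclusions | Study team (12.1.1) | Before freeze | Study team reviews unblinded data in-stream (10, 10.3.4) |
| AESI terms | Safety and Medical Governance, from SRT agreements (8.2) | Before unblinding | SRT reviews unblinded data in-stream (5.1) |

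**2. Was the in-stream review withdrawn?** No. SAP Table 1 cancels the futility interim. Protocol 10.3.4 treats in-stream review as a separate item, and Table 1 lists no change to it. SAP section 2.3 still calls the design sponsor-unblind.

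**3. How much judgement do the rules leave?** The protocol has 9 inclusion and 22 exclusion criteria, 31 in all. Rules 01 to 11 name inclusion 1 and 3 to 6 (5 criteria) and exclusion 1 to 15 (15 criteria), which makes 20. Rule 12 takes in a deviation from any of the other 31 − 20 = 11 (inclusion 2 and 7 to 9; exclusion 16 to 22), but only if it might affect the efficacy assessment. That condition calls for judgement.

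Two further choices arise because section 4 and 12.1.1 disagree:

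- Section 4 removes anyone with an exacerbation in the treatment phase; rule 13 removes only those whose exacerbation needed steroids.
- Section 4 removes those missing any of the Week 13 assessments. Rule 14 is worded around completing all of them, and can be read as missing at least one or as missing every one.

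Section 12.1.1 also cites version 2.0 of the deviation specification (31 August 2018) and defers to the latest version, while 4.1 cites version 6.0 (28 November 2019). The governing rules can therefore still move before the list is final.

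**4. What depends on the per-protocol set?** SAP 7.1.3 makes the Analysis Population primary and the per-protocol population supportive. Analysis Population membership requires dosing, a baseline and a post-baseline assessment, with no review of deviations. All five Bayesian tables (2.5, 2.14, 2.23, 2.28 and 2.34) are listed for the Analysis Population only. The exclusions therefore reach the per-protocol strength tables (2.2, 2.4, 2.7) and their counterparts for PROactive, SGRQ, SPPB and endurance-walk duration.

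**5. Scale.** The protocol's precision figure reproduces. With SD 10.9, the 90% half-width is t(0.95, 2n − 2) × 10.9 × √(2/n). This gives 8.45 at n = 10 and 5.81 at n = 20, against the stated 8.45 and 5.8.

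Removing k of n participants, each d points below the arm mean, raises that raw mean by kd/(n − k). With n = 20 and assumed values of d:

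- k = 1, d = 10.9 (one SD): 10.9/19 = 0.57
- k = 1, d = 20: 20/19 = 1.05
- k = 2, d = 20: 40/18 = 2.22

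As a ceiling, simulated normal samples of 20 with SD 10.9 shift on average by 1.08, 1.99 and 2.83 points when the lowest one, two or three values in one arm are dropped. All of these lie inside the 5.8-point half-width. They are raw means rather than the planned repeated-measures estimate, and they show sensitivity only.

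**The case against.** The strongest reply is that the protocol's wording is partly permissive. Section 7.4 speaks of members of the team, as appropriate, and of roles that may be included. Section 9.6 refers to blinded personnel, so some staff may have had no access and could be the blinded reviewers. Unblinding in the SAP may mean only the formal release of codes. Most of the 15 rules are factual checks, and the team is asked only to confirm that they are met. Exclusions are summarised in Table 1.7 and listed by participant and treatment in Listing 8. The AESI terms come from another function, and their groupings are already printed in SAP 12.6.3.

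Much of this stands and limits the harm. It does not resolve the conflict. Protocol sections 5.1 and 10 state the in-stream review without qualification, and nothing says who remained blinded. Formal code release would not explain why the meeting is called blinded, or why allocation is said to be unknowable beforehand.

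A reader might infer three stronger things, none of which the documents support:

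- *That exclusions were in fact chosen with knowledge of arm and response.* The documents allow by-arm review; none reports that one took place or who saw it.
- *That the per-protocol analysis is the only check on the primary result.* The SAP also plans a re-run without one centre (7.3.4.2) and a model with added baseline covariates (5.4.1).
- *That shifts of the size above would count against the 9-point target.* The probability tied to that target is calculated in the Analysis Population only.

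**Conclusion.** The point holds in a limited form. The SAP claims a blinded deviation review and places per-protocol confirmation with a team that the protocol allows to see individual and by-arm strength data, and no separation is described. The effect is confined to the supportive per-protocol analyses and, to a lesser degree, to AESI groupings resting on SRT agreements. The primary Analysis Population estimate and the planned probability of a difference of at least 9 points are unaffected. Within the per-protocol set, one or two discretionary exclusions in one arm could move that arm's raw mean by roughly 0.6 to 2.2 points under the assumed values. No document says how often such cases would arise.

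This rests on two assumptions: that the study team means the same body in both documents, and that no separate unblinding plan sets up a firewall. It should be corrected, but it does not threaten the main conclusion.

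**What to change.** 1. In SAP 4.1 and 12.1.1, have the per-protocol list signed off by reviewers documented as having no access to randomization codes or in-stream by-arm output. If no such reviewers exist, remove the word blinded and report that the decisions were made with in-stream access available.
2. Replace rule 12 with a closed list drawn from the 11 entry criteria that rules 01 to 11 leave out (inclusion 2 and 7 to 9; exclusion 16 to 22). Reconcile section 4 with 12.1.1 on exacerbations and on missing Week 13 assessments, and cite one version of the deviation specification.
3. In 3.1 and 8.2, state that unblinding means formal release of the codes for the final analysis, and that the protocol allowed the sponsor earlier in-stream access.

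The cost is SAP wording, a record of who had access and, where possible, reassignment of an existing review. No data collection or primary analysis changes. The downside is a less favourable description of blinding in the study report.

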## 5. CONSIDERATIONS FOR DATA ANALYSES AND DATA HANDLING CONVENTIONS

### 5.1. Study Treatment & Sub-group Display Descriptors

The analysis and summary will be separately analysed by gender. All graphical displays will present results for males and females on separate pages. Sex will be either a subtitle or subheading (“by” variable) on these displays.

For each efficacy analysis table, the results for female will displayed first and then repeated for male; for other tables, the summary will be presented in the order of female and male. Listings will be sorted by gender.

Treatment Group Descriptions			
Treatment Group		Data Displays for Reporting	
Code	Description	Description	Order in TLF
A	PTM GSK2881078 1.0mg	Placebo	1 - Female
B	GSK2881078 1.0 mg	GSK2881078 1.0 mg	2- Female
C	PTM GSK2881078 2.0mg	Placebo	1 - Male
D	GSK2881078 2.0 mg	GSK2881078 2.0 mg	2- Male

Treatment comparisons will be displayed as follows using the descriptors as specified and separated by gender:

Female: GSK2881078 1.0 mg vs Placebo

Male: GSK2881078 2.0 mg vs Placebo

### 5.2. Baseline Definitions

Parameter	Study Assessments Considered as Baseline			Baseline Used in Data Display
	Screening	Day -9	Day 1 (Pre-Dose)	
Efficacy				
Leg Strength	X		X	whichever is latest*
Incremental Shuttle Walk Test		X	X	whichever is higher
Endurance Shuttle Walk Test			X	Day 1
Dual-energy X-ray Absorptiometry (DXA)			X	Day 1
Short Physical Performance Battery (SPPB)	X		X	whichever is latest*
COPD Assessment Test (CAT)			X	Day 1
Patient Global Rating of Severity (PGRS)			X	Day 1
St George Respiratory			X	Day 1

Parameter	Study Assessments Considered as Baseline			Baseline Used in Data Display
	Screening	Day -9	Day 1 (Pre-Dose)	
Questionnaire COPD (SGRQ-c)				
PROactive Physical Activity	X	X		See detail below**
Spirometry	X		X	whichever is latest*
Sniff Nasal Inspiratory Pressure (SnIP)	X		X	whichever is latest*
Safety				
Vital Signs	X		X	whichever is latest*
12-lead ECG	X		X	whichever is latest*
Haematology	X		X	whichever is latest*
Clinical Chemistry	X		X	whichever is latest*
Urinalysis	X		X	whichever is latest*
hsCRP, Fibrinogen			X	Day 1
Lipid panel	X		X	whichever is latest*
PSA	X		X	whichever is latest*
HbA1c	X			screening
Exploratory				
Cardiac and liver MRI			X	Day 1
Handgrip strength	X		X	whichever is latest*
Reproductive Tissue Biomarkers			X	Day 1
Bone Biomarkers			X	Day 1
***Exploratory Biomarkers			X	Day 1
***Monitored home exercise program		X	X	whichever is latest*

\*Baseline value will be the latest pre-dose assessment with a non-missing value, including those from unscheduled visits. If time is not collected, Day 1 assessments are assumed to be taken prior to first dose and used as baseline.

\*\*Baseline will be the average of the data collected from the 7-day period after Day -9 device dispense.

\*\*\*Exploratory Biomarkers and home exercise program will be analysed separately and will not be reported as part of this study Statistical Analysis Complete reporting.

Unless otherwise stated, if baseline data is missing no derivation will be performed and baseline will be set to missing.

### 5.3. Multicentre Studies

In this multicentre global study, enrolment will be presented by investigative site. There is no analysis planned by center/investigative site.

